##### 1.2.1.3.1 Clinical Pharmacokinetics of Nivolumab

The pharmacokinetics (PK) of nivolumab was studied in subjects over a dose range of 0.1 to 10 mg/kg administered as a single dose or as multiple doses of nivolumab every 2 or 3 weeks.

The geometric mean (% CV%) clearance (CL) was 9.5 mL/h (49.7%), geometric mean volume of distribution at steady state (Vss) was 8.0 L (30.4%), and geometric mean elimination half-life (t1/2) was 26.7 days (101%). Steady-state concentrations of nivolumab were reached by 12 weeks when administered at 3 mg/kg Q2W, and systemic accumulation was approximately 3-fold. The exposure to nivolumab increased dose proportionally over the dose range of 0.1 to 10 mg/kg administered every 2 weeks. Additionally, nivolumab has a low potential for drug-drug interactions.

The clearance of nivolumab increased with increasing body weight. The PPK analysis suggested that the following factors had no clinically important effect on the CL of nivolumab: age (29 to 87 years), gender, race, baseline LDH, PD-L1. A PPK analysis suggested no difference in CL of nivolumab based on age, gender, race, solid tumor type, baseline tumor size, and hepatic impairment. Although ECOG status, baseline glomerular filtration rate (GFR), albumin, body weight, and mild hepatic impairment had an effect on nivolumab CL, the effect was not clinically meaningful. When nivolumab is administered in combination with ipilimumab, the CL of nivolumab was increased by 24%, whereas there was no effect on the clearance of ipilimumab.

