  - d. Hemoglobin  $> 9$  g/dL
  - e. Serum creatinine  $\leq 1.5 \times$  upper limit of normal (ULN) or creatinine clearance (CrCl)  $\geq 40$  mL/min according to the Cockcroft-Gault formula or local institutional standard method
  - f. Aspartate aminotransferase (AST) and alanine aminotransferase (ALT)  $\leq 3 \times$  ULN
  - g. Total bilirubin  $\leq 1.5 \times$  ULN (except subjects with Gilbert Syndrome, who can have total bilirubin  $< 3.0$  mg/dL)
35. Women of child-bearing potential (WOCBP) and men able to father a child must agree to use highly effective contraception (any contraceptive method with a failure rate of less than 1% per year) while on study drug and for 23 weeks (for women) or 31 weeks (for men) after the last dose of study drug.
  - a. WOCBP must have a negative serum or urine pregnancy test within 24 hours of initiation of study drug.
  - b. WOCBP is defined as any female who has experienced menarche and who has not undergone surgical sterilization (hysterectomy or bilateral oophorectomy) or who is not postmenopausal. Menopause is defined clinically as 12 months of amenorrhea in a woman over 45 in the absence of other biological or physiological causes. In addition,

CONFIDENTIAL

This material is the property of the NYU School of Medicine. Do not disclose or use except as authorized in writing by the study sponsor

women under the age of 55 must have a documented serum follicle stimulating hormone (FSH) level less than 40 mIU/mL to be defined as post-menopausal.

- c. WOCBP receiving nivolumab will be instructed to adhere to contraception for a period of 23 weeks after the last dose of investigational product. Men receiving nivolumab and who are sexually active with WOCBP will be instructed to adhere to contraception for a period of 31 weeks after the last dose of investigational product. These durations have been calculated using the upper limit of the half-life for nivolumab (25 days) and are based on the protocol requirement that WOCBP use contraception for 5 half-lives plus 30 days and men who are sexually active with WOCBP use contraception for 5 half-lives plus 90 days.

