#### 6.2.4 Treatment Discontinuation Criteria

For all subjects, global deterioration of health status requiring discontinuation of treatment without objective evidence of disease progression at that time should be reported as 'symptomatic deterioration' in the source data and in the case report form. Every effort should be made to document objective progression (i.e., radiographic confirmation) even after discontinuation of treatment.

The assessment for discontinuation of ipilimumab should be made separately from the assessment made for discontinuation of nivolumab. Although there is overlap among the discontinuation criteria, if

CONFIDENTIAL

This material is the property of the NYU School of Medicine. Do not disclose or use except as authorized in writing by the study sponsor

discontinuation criteria are met for ipilimumab but not for nivolumab, treatment with nivolumab may continue if ipilimumab is discontinued.

If a subject meets criterion for permanent discontinuation and investigator is unable to determine whether the event is related to both or one study drug, the subject should discontinue both nivolumab and ipilimumab and be taken off the treatment phase of the study.

Note: Infusion-related reactions, hypersensitivity reactions (Grades 1 to 4), should be handled according to Section 6.2.8.

Note: See Section 8.1, Adverse Event Definitions, for expected AEs related to nivolumab and ipilimumab. Brain edema is an expected AE related to RT.

Decision to discontinue is determined at the time that the treatment discontinuation criteria is met. End of treatment procedures should follow as outlined in 6.7.

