### **Pregnancy**

If, following initiation of the investigational product, it is subsequently discovered that a study participant is pregnant or may have been pregnant at the time of investigational product exposure, including during at least 5 half-lives after product administration (within 5 months after the last dose of study drug for a female subject and within of 7 months after the last dose of study drug for a male subject), the investigational product will be permanently discontinued in an appropriate manner (eg, dose tapering if necessary for participant).

The investigator must immediately notify [[contact]](mailto:[contact]) of this event via the **Pregnancy Surveillance Form** [provided upon request from BMS] in accordance with SAE reporting procedures. The investigator must also immediately notify the Sponsor/Overall PI of the event.

Protocol-required procedures for study discontinuation and follow-up must be performed on the participant. Follow-up information regarding the course of the pregnancy, including perinatal and neonatal outcome and, where applicable, offspring information must be reported on the Pregnancy Surveillance Form.

Any pregnancy that occurs in a female partner of a male study participant should be reported to BMS. Information on this pregnancy will be collected on the Pregnancy Surveillance Form. In order for Sponsor or designee to collect any pregnancy surveillance information from the female partner, the female partner must sign an informed consent form for disclosure of this information.

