##### **Initial Report: within 24 hours of awareness of the event:**

The following events must be reported to the study sponsor by telephone within 24 hours of awareness of the event:

- Unanticipated problems related to study participation,
- Serious adverse events, regardless of whether they are unexpected.
- Overdose of Study Drug, defined in Section 8.1.
- Pregnancy: Although pregnancy is not considered an AE, it is the responsibility of the investigator to report to the Sponsor (or designee), by telephone within 24 hours of identification, any pregnancy occurring in a female subject or female partner of a male subject, during the study or within 5 months after the last dose of study drug for a female subject or within 7 months after the last dose of study drug for a male subject. Any complication of pregnancy affecting a female subject or female partner of a male subject, and/or fetus and/or newborn must be reported as an SAE. All pregnancy outcomes will be followed as described in Section 8.1. Pregnancies must also be reported on a Pregnancy Surveillance Form to BMS immediately as described in Section 8.1.
- Exposure during Pregnancy or Breastfeeding (even if not associated with an adverse event)
- Occupational exposure (even if not associated with an adverse event)
- Potential drug-induced liver injury (DILI): These events are considered important medical events and should be reported as SAEs. See Section 8.1 for DILI definition.

In the event the investigator is informed of an SAE that occurs after 30 days after the last dose of study treatment, only those SAEs or other AEs of concern deemed by the investigator to be related to study treatment will be reported to the sponsor. The investigator should make every effort to obtain follow-up information on the outcome of a treatment-related SAE until the event is considered chronic and/or stable.

Additionally, an **FDA Form 3500 (MEDWATCH Form)** must be completed by the investigator and faxed to the study **Sponsor/Overall PI** within 24 hours. The investigator shall maintain a copy of the MEDWATCH Form on file at the study site or can be obtained from the FDA website:  
<http://www.fda.gov/safety/medwatch/howtoreport/downloadforms/default.htm>.

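### The contraception periods rest on a 25-day nivolumab half-life labelled an upper limit, below the 26.7-day geometric mean the protocol itself reports; for nivolumab alone the protocol's rule then gives 24 and 32 weeks, not 23 and 31

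*Combined protocol and SAP*

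**What the plan says.** The contraception criterion appears in the Synopsis (Inclusion Criteria, item 12) and again in Section 4.1. Its lead sentence requires highly effective contraception on study drug and "for 23 weeks (for women) or 31 weeks (for men) after the last dose of study drug". Item c gives the derivation: "These durations have been calculated using the upper limit of the half-life for nivolumab (25 days". It then states the rule: "WOCBP use contraception for 5 half-lives plus 30 days", and five half-lives plus 90 days for men who are sexually active with such women.

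Section 1.2.1.3.1 (Clinical Pharmacokinetics of Nivolumab) reports that the geometric mean elimination half-life "was 26.7 days (101"; the bracketed figure is the CV in percent. The same section adds that, when ipilimumab is given too, "the CL of nivolumab was increased by 24" percent.

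Section 6.2.4 has the two drugs assessed separately for discontinuation, and "treatment with nivolumab may continue if ipilimumab is discontinued".

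**The concern.** An upper limit cannot lie below the average of the same quantity. Either 25 days is not an upper limit, or the half-life in the pharmacokinetics section is not the relevant one. No text says which, and no source is given for the 25 days.

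The durations are an eligibility condition and a standing instruction to patients. Section 1.2.1.2 describes nivolumab as a selective developmental toxicant in monkeys, so the input to this rule should agree with the protocol's own pharmacokinetic data. At the half-life the protocol reports, the stated periods do not meet the rule the protocol sets for itself. No efficacy analysis is involved.

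**Working it through.** **Inputs**
- Half-life used for the rule: 25 days (Section 4.1 and Synopsis, item c).
- Half-life reported: geometric mean 26.7 days, CV 101% (Section 1.2.1.3.1).
- Rule: 5 × half-life + 30 days for women, + 90 days for men (item c).
- Stated periods: 23 weeks = 161 days and 31 weeks = 217 days.
- Nivolumab clearance with ipilimumab: 24% higher (Section 1.2.1.3.1).

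**Reproducing the plan's figures at 25 days**
- Women: 5 × 25 + 30 = 155 days = 22.14 weeks, rounded up to 23.
- Men: 5 × 25 + 90 = 215 days = 30.71 weeks, rounded up to 31.

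Both figures reproduce. Rounding to the nearest week would give 22 for women, so the protocol rounds up.

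**The same rule at 26.7 days** (5 × 26.7 = 133.5 days)
- Women: 133.5 + 30 = 163.5 days = 23.36 weeks, rounded up to 24 (168 days). Shortfall now: 163.5 − 161 = 2.5 days.
- Men: 133.5 + 90 = 223.5 days = 31.93 weeks, rounded up to 32 (224 days). Shortfall now: 223.5 − 217 = 6.5 days.

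**Longest half-life that meets the rule**
- At 23 and 31 weeks: (161 − 30)/5 = 26.2 days and (217 − 90)/5 = 25.4 days.
- At 24 and 32 weeks: (168 − 30)/5 = 27.6 days and (224 − 90)/5 = 26.8 days.

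**What the shortfall amounts to**
- Margin left after five half-lives: 161 − 133.5 = 27.5 of the 30 added days; 217 − 133.5 = 83.5 of the 90.
- Residual drug at the end of the period, by simple exponential decay at 26.7 days. Women: 0.5^(161/26.7) = 1.53%, against 0.5^(163.5/26.7) = 1.43% under the rule. Men: 0.5^(217/26.7) = 0.36%, against 0.5^(223.5/26.7) = 0.30%.

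**On the combination** (assumption: half-life falls in proportion to the rise in clearance)
- Half-life: 26.7/1.24 = 21.5 days.
- Women: 137.7 days needed, so 161 leaves 23.3 to spare.
- Men: 197.7 days needed, so 217 leaves 19.3 to spare.

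**The label** (assumption: half-life is log-normal with CV 101%)
- Sigma = √ln(1 + 1.01²) = 0.839.
- Share of patients above 25 days: about 53% with a geometric mean of 26.7 days, and about 43% with 21.5 days. On either figure, 25 days is a central value.

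**The case against.** The strongest reply is that every patient starts on nivolumab plus ipilimumab, and on the combination the present periods have about three weeks to spare. This stands, given the proportionality assumption, and it limits the shortfall mainly to patients who go on with nivolumab alone. A reader might infer that the whole trial population falls short of the rule; the documents do not support that. The argument does not rescue the text, however. Item c does not invoke the combination, and nivolumab alone is a planned situation. Some stopping criteria are stricter for ipilimumab: AST or ALT above 5 × ULN stops it after more than 2 weeks (Section 6.2.4.2), but stops nivolumab only after more than 4 (Section 6.2.4.1).

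A second reply is that 26.7 days is itself uncertain. From the reported clearance (9.5 mL/h) and volume (8.0 L), a one-compartment approximation gives ln 2 × 8000/9.5 = 584 hours, or 24.3 days. The Investigator's Brochure, to which the protocol refers for detail, may contain the origin of the 25 days. Both points are fair. Yet an approximation near 24 days also shows 25 to be a typical value, and the protocol reports 26.7, not 24.3.

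Third, a period based on the mean is not conservative either: under the log-normal assumption half of the patients on nivolumab alone exceed 26.7 days. That is correct, so 24 and 32 weeks must not be presented as restoring an upper limit. They make the calculation agree with the reported pharmacokinetics. Relabelling 25 days alone would remove the false description but leave the rule unmet at the reported mean for nivolumab alone.

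A reader might also infer that the pregnancy windows are wrong. Section 8.1 uses "within 5 months after the last dose of study drug for a female subject and within of 7 months after the last dose", and Section 8.4.1 uses "within 5 months after the last dose of study drug for a female subject or within 7 months after the last dose". Five calendar months (150–153 days) and seven (212–215 days) end 8–11 and 2–5 days before 161 and 217 days. But Section 8.1 bases its window on at least five half-lives, without the added 30 or 90 days. Five half-lives at 26.7 days is 133.5 days, which both windows cover. Section 8.4.1 also includes pregnancies during the study, and Sections 6.8.3 and 6.10.1 support reading that as including follow-up after treatment.

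**Conclusion.** The point holds as a minor inconsistency in a safety input. Calling 25 days an upper limit is incompatible with the geometric mean in Section 1.2.1.3.1; this conclusion needs no distributional assumption. At that mean, the protocol's rule gives 24 and 32 weeks, and the stated periods fall 2.5 days (women) and 6.5 days (men) short.

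The shortfall applies mainly to patients who continue nivolumab without ipilimumab. That restriction rests on half-life falling in proportion to the clearance increase. The practical consequence is slight, because the shortfall comes wholly out of the added 30 or 90 days. The pregnancy windows in Sections 8.1 and 8.4.1 are not in error.

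**What to change.** In the contraception criterion, in both the Synopsis and Section 4.1 (lead sentence and item c):
- delete the description of the half-life as an upper limit;
- state that the calculation uses the 26.7-day geometric mean for nivolumab alone from Section 1.2.1.3.1;
- set the durations to 24 weeks for women and 32 weeks for men.

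The cost is one extra week of contraception for each sex and a wording change in the protocol and consent form.

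As optional tidying, the 5- and 7-month windows in Sections 8.1 and 8.4.1 could be set to the same 24 and 32 weeks. This would lengthen them by 15–18 days (168 minus 150–153) for women and 9–12 days (224 minus 212–215) for men.

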## **4.2 Exclusion Criteria**

- 1. Prior use of any standard or investigational anti-tumor therapy other than surgery
- 2. Planned participation in another study of an investigational agent or investigational device or planned use of any other agent or therapeutic device intended for therapy of glioma.
- 3. Infratentorial tumors.
- 4. Patients with >1 cm midline shift on postoperative, baseline brain MRI.
- 5. Diffuse leptomeningeal gliomatosis.
- 6. Known mutation of the *IDH1* or *IDH2* genes in the tumor, since glioblastomas with these mutations have different biology and are associated with improved prognosis.
  - a. Documentation that no *IDH1* or *IDH2* mutations are present in the tumor by a CLIA approved laboratory is required prior to initiation of study treatment.
- 7. Intracranial hemorrhage grade >1 not attributable to recent neurosurgery.
- 8. Systemic treatment with either immunosuppressive doses of corticosteroids (> 10 mg daily prednisone equivalents) or other immunosuppressive medications within 14 days of study drug administration.
  - a. Subjects on a standard high-dose steroid taper after craniotomy or stereotactic biopsy may have received a higher dose of corticosteroids within 14 days of registration, however must be at a dose < 10 mg daily prednisone or bioequivalent per day within 5 days prior to initiation of study drug.
  - b. Administration of steroids through a route known to result in a minimal systemic exposure [i.e., intranasal, intraocular, inhaled, topical, or local injection (e.g., intra-articular injection) corticosteroids (<5% of body surface area)] are permitted in the absence of active autoimmune disease.

CONFIDENTIAL

This material is the property of the NYU School of Medicine. Do not disclose or use except as authorized in writing by the study sponsor

- c. Subjects requiring adrenal replacement with corticosteroids are eligible if the steroids are at doses  $\leq$  10 mg prednisone or bioequivalent per day in the absence of active autoimmune disease.
- d. Steroids as premedication for hypersensitivity reactions (e.g., CT scan premedication) are allowed.

2. Active autoimmune disease that might deteriorate when receiving an immuno-stimulatory agent. The following conditions are not exclusions (subjects with the following conditions are permitted):

- a. Patients with diabetes type I, vitiligo, residual hypo- or hyperthyroidism due to autoimmune condition only requiring hormone replacement, or psoriasis not requiring systemic immunosuppressive treatment, or autoimmune conditions not expected to recur in the absence of an external trigger.
- 3. Prior organ transplantation, including allogeneic stem cell transplantation.
- 4. Known history of, or any evidence of active, non-infectious pneumonitis within the last 5 years.
- 5. Known severe (NCI-CTCAE v4.03 Grade 3 or 4) infusion-related allergy or acute hypersensitivity reaction attributed to any monoclonal antibody, any history of anaphylaxis, or uncontrolled asthma (that is, 3 or more features of partially controlled asthma).
- 6. Unable tolerate an MRI, or have a contraindication to MRI.
- 7. Active infection requiring systemic therapy.
- 8. Known history of testing positive for human immunodeficiency virus (HIV) or known acquired immunodeficiency syndrome.
- 9. Positive test for hepatitis B virus surface antigen (HBV sAg) or hepatitis C virus (HCV antibody) indicating acute or chronic infection.
- 10. Vaccination within 4 weeks of the first dose of study drug and while on trials is prohibited except for administration of inactivated vaccines. Note: Seasonal influenza vaccines for injection are generally inactivated flu vaccines and are allowed; however intranasal influenza vaccines (e.g., Flu-Mist®) are live attenuated vaccines, and are not allowed.
- 11. Clinically significant (i.e., active) cardiovascular disease: cerebral vascular accident/stroke ( $< 6$  months prior to enrollment), myocardial infarction ( $< 6$  months prior to enrollment), unstable angina, congestive heart failure ( $\geq$  New York Heart Association Classification Class II), or serious cardiac arrhythmia requiring medication.
- 12. Patients with another active cancer [excluding basal cell carcinoma, cervical carcinoma *in situ* or melanoma *in situ*]. Prior history of other cancer is allowed, as long as there was no active disease within the prior 2 years.
- 13. All other unstable, severe, or chronic medical or psychiatric conditions including colitis, inflammatory bowel disease, pneumonitis, pulmonary fibrosis, recent (within the past year) or active suicidal ideation or behavior, known alcohol or drug abuse, or laboratory abnormalities that may increase the risk associated with study participation or study treatment administration or may interfere with the interpretation of study results and, in the judgment of the investigator, would make the patient inappropriate for entry into this study.

### **4.3 Prior and Concomitant Therapy**

#### **4.3.1 Concomitant Medications**

Any treatment administered from the time of informed consent until 30 days after the last study treatment will be considered concomitant treatment. This includes medications and other therapies for which administration started before the study and will continue during the study, as well as any therapies started in the follow-up period to treat a study-drug-related AE.

CONFIDENTIAL

This material is the property of the NYU School of Medicine. Do not disclose or use except as authorized in writing by the study sponsor

All concomitant treatments must be recorded in the study CRF with the generic name, dose, dose unit, frequency, indication, and start/stop date, as appropriate.

#### 4.3.2 Permitted Concomitant Medications

All treatments that the investigator considers necessary for a subject's welfare may be administered at the discretion of the investigator in keeping with the community standards of medical care.

Subjects are permitted the use of topical (<5% of body surface area), ocular, intra-articular, intranasal, and inhalational corticosteroids (with minimal systemic absorption). Adrenal replacement steroid doses > 10 mg daily of prednisone or bioequivalent are permitted. A brief (less than 3 weeks) course of premedication corticosteroids for prophylaxis (eg, contrast dye allergy) or for treatment of non-autoimmune conditions (eg, delayed-type hypersensitivity reaction caused by a contact allergen) is permitted. Antihistamines and other non-steroidal anti-allergy medications are also permitted.

During the study, systemic steroids at doses > 10 mg daily of prednisone or bioequivalent is also permitted for management of symptoms related to intracranial/brain edema or central nervous system radiation necrosis, however bevacizumab is preferred over corticosteroids for these conditions. See Rules for Intracranial and Brain Edema in Section 6.2.5 for guidelines on management of symptoms related to intracranial/brain edema, bevacizumab administration, and corticosteroid use in this setting.

